1 BACKGROUND AND RATIONALE

Title

Observational, correlational study aimed to identify healthy elderly subjects with Alzheimer pathology more efficiently.

Short Title

Observational, correlational study to identify Alzheimer pathology in healthy elderly.

[figure not shown]
Background & Rationale

As new disease-modifying therapies for Alzheimer's disease (AD) enter clinical trials, identifying the disease at a clinical stage where the pathological injury is not too severe to allow functionally meaningful recovery, or at least stabilization, is a major issue of current research [1]. New empirical criteria aim at defining early clinical, biochemical, and metabolic markers of AD before the criteria of dementia are clinically fulfilled [2]. Identification of the pre-dementia phase of AD is crucial to allow progress of new treatments designed to intervene in the disease process at the earliest possible stage.

While the definite diagnosis for AD can only be made post-mortem by investigating the presence of amyloid beta $(A\beta)$ plaques and neurofibrillary tangles, recent advances in neuroimaging, cerebrospinal fluid (CSF) assays, and other fluid biomarkers now provide the ability to detect evidence of the AD pathophysiological process in vivo [3]. Furthermore, emerging data in otherwise healthy elderly individuals suggest that biomarker evidence of $A\beta$ accumulation and neurofibrillary tangles are associated with functional and structural brain alterations, consistent with the patterns of abnormality seen in patients with mild cognitive impairment (MCI) and AD prior to the clinical expression of symptoms [4]. These observations are confirmed by clinical cohort studies which suggest that there may be very subtle cognitive alterations that are detectable years before meeting clinical criteria for MCI, and which predict progression to AD [5].

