1.1.4 Sample Size Justification

This is an exploratory study, therefore the samples size is not based on statistical considerations. The aim for this study is to enroll 200 subjects. The assays to determine $A\beta$ from CSF are well established methods and the sample size justification for this current study is therefore based on previous research on amyloid pathology in CSF. In this study we select elderly at the age of 65 and higher of which at least a hundred will be above the age of 70. According to Jansen et al., (2015) we can expect at least 19% amyloid pathology in a 65+ population and 23% amyloid pathology among cognitively healthy 70+ elderly subjects. As we expect more responsiveness for study participation from elderly between the age of 65 till 70, based on our experience with previous studies in this age range, at least 100 subjects of >70 years old will be included in this study to be able to differentiate between age, which results in approximately 23 A β positive subjects versus approximately 77 A β negative subjects in this elderly age group. Along with approximately 19 A β positive subjects versus approximately 81 A β negative subjects in the age group 65-70 we expect to find at least 42 A β positive healthy elderly subjects. Based on previous comparable studies, these numbers are considered appropriate for a correlational study aimed at defining an algorithm [22, 23].

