9.8 CNS and biochemical endpoints

9.8.1 NeuroCart

All parameters will be listed by subject.

Parameters will initially be analysed without transformation, but if the data suggest otherwise, log-transformation may be applied.

Descriptive statistics will be used to summarize the data. Data will be graphically processed for visual inspection.

In order to develop an algorithm that can classify the subjects between ADpath+ and ADpath- there will be a two-step procedure. In the first step 500 bootstrap samples will be generated out of the original data and logistic regression with LASSO penalization (in order to account for the expected small event per variable ratio) in each of the bootstrap samples with all the candidate variables (CNS and biochemical outcome variables, age and educational level) will be performed. Out of all the candidate variables the ones that consistently and most frequently appear in the bootstrap models will be selected. Hence, in this first step the variable selection will take place. In the second step another 500 bootstrap samples will be generated and logistic regression will be performed (with penalization if necessary) in each of the bootstrap samples. This time only the variables that were selected in step 1 will be entered in the model. The estimates out of all the bootstrap models will be averaged and used in order to obtain predictions in the original data. Step two will result in the bootstrap-corrected predictions that will be assessed in terms of calibration (calibration slope), discrimination (c-index) and squared mean prediction error.

To investigate the relationship between biomarkers and gene carriers and NeuroCart scores, correlations and regression analyses will be used.

NeuroCart scores will be analysed with an analysis of variance (ANOVA) and/or multivariate analysis of variance (MANCOVA) to estimate differences between the groups of elderly with different Aβ status.

The intra- and inter-individual diurnal fluctuation will be investigated with mixed-model analysis.

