9.8.2 Inferential methods

The study is exploratory and no formal null hypothesis is set. No adjustments for multiple comparisons will be applied.

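### NeuroCart differences by Aβ status are planned with ANOVA/MANCOVA at an expected 42 versus 158 subjects; if the spread differs between groups, the default pooled variance misstates the precision of each difference

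*Protocol*

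**What the plan says.** Section 9.8.1 of the protocol, repeated in the synopsis and in section 1.1.9, gives the method for comparing NeuroCart scores by Aβ status: "NeuroCart scores will be analysed with an analysis of variance (ANOVA) and/or multivariate analysis of variance (MANCOVA) to estimate differences between the groups". It names no covariates and does not address unequal variances. Scores are first analysed untransformed, data are inspected graphically, and log-transformation may follow if the data suggest it.

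The group sizes come from section 1.1.4. The total is fixed by "The aim for this study is to enroll 200 subjects". The forecast is "approximately 23 A β positive subjects versus approximately 77 A β negative subjects" above age 70 and "approximately 19 A β positive subjects versus approximately 81 A β negative subjects" at age 65-70, so that "we expect to find at least 42 A β positive healthy elderly subjects".

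On inference, section 9.8.2 says "The study is exploratory and no formal null hypothesis is set" and that no multiplicity adjustment will be made. No significance level, interval level or NeuroCart SD is given anywhere in the protocol.

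**The concern.** ANOVA and MANCOVA, as usually run, estimate a single residual variance (or covariance matrix) across both groups. With equal group sizes this does little harm even when the spreads differ. With nearly four negatives for each positive, the pooled variance is mostly that of the negative group, while the uncertainty of the difference comes mostly from the small positive group. If the positives are more variable, the standard error is too small; if they are less variable, it is too large.

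What is at stake is the precision reported for each NeuroCart difference. Section 6.2 lists 51 NeuroCart scores, counting the EEG and eye-movement measures. The SD ratio need not be the same for all of them, so the error could run in different directions for different scores. Readers who rank the scores by estimate and precision would then not be comparing them on one footing.

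**Working it through.** **Inputs from the protocol (section 1.1.4).** Positives: 23 + 19 = 42. Negatives: 77 + 81 = 158. Total 200. Ratio 158/42 = 3.76. The protocol's figure of 42 is reproduced.

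**Assumptions, not in the protocol.** Two-sided 5% level and 95% interval; normal data; no covariates. Let r be the SD in positives divided by the SD in negatives, with the negative SD set to 1.

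**Formulas.** Two-group ANOVA is the pooled t test on 198 degrees of freedom.
- Pooled variance: (41r² + 157)/198
- Variance of the difference as ANOVA estimates it: pooled variance × (1/42 + 1/158) = pooled variance × 0.03014
- True variance of the difference: r²/42 + 1/158
- k = square root of (estimated/true), the factor by which the interval has the wrong width
- Actual size ≈ 2[1 − Φ(1.972k)]

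**Worked case, r = 1.5.** Pooled variance (41 × 2.25 + 157)/198 = 1.259. Estimated variance 1.259 × 0.03014 = 0.0379. True variance 2.25/42 + 1/158 = 0.0599. k = √(0.0379/0.0599) = 0.796. Size ≈ 2[1 − Φ(1.57)] = 0.1165; simulation gives 11.9%.

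**Range of r, 42 versus 158 (sizes by simulation; repeat runs agree to about 0.1 percentage point).**

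| SD ratio r | Width factor k | Pooled test, actual size | Coverage of nominal 95% interval | Welch test, actual size |
|---|---|---|---|---|
| 0.8 | 1.137 | 2.6% | 97.4% | 5.0% |
| 0.9 | 1.063 | 3.7% | 96.3% | 5.0% |
| 1.0 | 1.000 | 5.0% | 95.0% | 5.0% |
| 1.1 | 0.946 | 6.3% | 93.7% | 4.9% |
| 1.25 | 0.879 | 8.4% | 91.6% | 5.0% |
| 1.5 | 0.796 | 11.9% | 88.1% | 5.0% |

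**Is the imbalance the cause?** With 100 versus 100 and r = 1.5, the pooled variance is (2.25 + 1)/2 = 1.625, the estimated variance 1.625 × 2/100 = 0.0325, and the true variance 2.25/100 + 1/100 = 0.0325. Then k = 1 and the size stays at about 5%. So the distortion comes from the unequal group sizes.

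**How large might r be?** Suppose half the positives are shifted by δ SD and the rest are unaffected. The variance in positives becomes 1 + 0.5 × 0.5 × δ² = 1 + 0.25δ².
- δ = 0.5: r = √1.0625 = 1.03
- δ = 1: r = √1.25 = 1.12, k = 0.936, error rate about 6.5%
- r = 1.5 would need δ = √(1.25/0.25) = 2.24, which is not a subtle change

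**Price of allowing unequal variances.** At equal SDs and a true difference of 0.5 SD, simulated power is 81.6% pooled and 80.9% Welch, a loss of 0.7 percentage points. At r = 0.8 and a difference of 0.4 negative-group SDs, Welch raises power from 68% to 77%.

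**The case against.** The strongest objection is that the protocol names only a family of methods. Equal variance is the default of that family, not the protocol's wording, and the variance structure could be settled in a SAP that is not shown. This limits the weight of the point but does not remove it. The protocol does fix the method, and it forecasts group sizes at which the default is fragile.

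Four further objections stand in part.

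- **No tests are set.** A reader might infer that stated 5% tests and 95% intervals are wrong. The protocol states neither level and sets no null hypothesis. It does set out to estimate differences, however, and an estimate needs a sound standard error.
- **Unequal spread is not shown.** A reader might infer from the background that the positive group must be a mix of affected and unaffected subjects. Section 1 says only that "there may be very subtle cognitive alterations that are detectable years before meeting clinical criteria for MCI". Subjects with MMSE of 24 or below or a diagnosed cognitive disorder are also excluded. Moreover, a mixture, or spread that rises with the mean, makes the spreads differ only when the means differ too. The relevant harm is then interval coverage, more than false differences under no effect. The coverage figures above do not depend on the true difference.
- **Log-transformation is allowed.** It may well cure spread that rises with the mean. It is optional, and it is undefined for scores that can be zero or negative: the N-back accuracy score, post-error slowing and error counts.
- **Other analyses use the same scores.** A reader might take this as the only look at NeuroCart and Aβ. It is the only planned ANOVA-type comparison of group means. The NeuroCart variables also enter the LASSO logistic model, which does not assume equal group variances, and the correlation and regression analyses.

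**Conclusion.** The point holds conditionally and is minor. For groups expected at about 42 and 158, the planned method by default relies on equal variances, and the protocol offers only an optional log-transformation against unequal spread. If the SD ratio lies between 0.8 and 1.5, a nominal 5% error rate becomes roughly 2.6% to 11.9%. For ratios of 0.9 to 1.1 it is only 3.7% to 6.3%. Under the mixture worked above, with shifts of up to 1 SD, it reaches about 6.5%.

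These figures rest on an assumed 5% level, assumed SD ratios, normal data and a comparison without covariates. The documents do not support the stronger reading that the NeuroCart results will be materially wrong. Nor do they support abandoning MANCOVA, since its behaviour was not examined here. The comparison is exploratory, and the development of the algorithm does not depend on it.

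**What to change.** In section 9.8.1, add that each NeuroCart difference by Aβ status will be estimated, after any log-transformation, from the same linear model with residual variance allowed to differ by Aβ status, and reported with its confidence interval at a stated level. In SAS this is PROC MIXED with a REPEATED statement and GROUP= Aβ status, with Satterthwaite or Kenward-Roger degrees of freedom. If the model has no covariates, the Welch test is enough; if it has covariates, they should stay in the model, since a plain Welch test would drop them.

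The cost is one sentence and one option in a procedure already named in section 9.4. Power falls by under 1 percentage point if the variances are in fact equal. One drawback remains: the unequal-variance test is somewhat liberal for strongly skewed scores left untransformed (about 7% for lognormal data with log-SD 1). The decision on transformation should therefore come first.

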9.8.2 Inferential methods

The study is exploratory and no formal null hypothesis is set. No adjustments for multiple comparisons will be applied.

9.9 Exploratory analyses and deviations

Exploratory data-driven analyses can be performed with the caveat that any statistical inference will not have any confirmatory value.

Deviations from the original statistical plan will be documented in the article.

10 GOOD CLINICAL PRACTICE, ETHICS AND ADMINISTRATIVE PROCEDURES

10.1 Good clinical practice

10.1.1 Ethics and good clinical practice

The investigator will ensure that this study is conducted in full compliance with the protocol, the principles of the Declaration of Helsinki, ICH GCP guidelines, and with the laws and regulations of the country in which the clinical research is conducted.

10.1.2 Ethics committee / institutional review board

The investigator will submit this protocol and any related documents to an Ethics Committee (EC) and the Competent Authority (CA). Approval from the EC and the statement of no objection from the CA must be obtained before starting the study, and should be documented in a dated letter/email to the investigator, clearly identifying the trial, the documents reviewed and the date of approval. A list of EC members must be provided, including the functions of these members. If study staff were present, it must be clear that none of these persons voted.

Modifications made to the protocol after receipt of the EC approval must also be submitted as amendments by the investigator to the EC in accordance with local procedures and regulations.

10.1.3 Informed consent

It is the responsibility of the investigator to obtain written informed consent from each individual participating in this study after adequate explanation of the aims, methods, objectives and potential hazards of the study. The investigator must also explain to the subjects that they are completely free to refuse to enter the study or to withdraw from it at any time for any reason.

The Informed Consent and Subject Information will be provided in Dutch.

10.1.4 Insurance

The investigator has a liability insurance which is in accordance with article 7, subsection 6 of the WMO.

The investigator (also) has an insurance which is in accordance with the legal requirements in the Netherlands (Article 7 WMO and the Measure regarding Compulsory Insurance for Clinical Research in Humans of 23rd June 2003). This insurance provides cover for damage to research subjects through injury or death caused by the study.

- € 650,000.- (i.e., six hundred and fifty thousand Euro) for death or injury for each subject who participates in the Research;
- € 5,000,000.- (i.e., five million Euro) for death or injury for all subjects who participate in the Research;
- € 7,500,000.- (i.e., seven million and five hundred thousand Euro) for the total damage incurred by the organisation for all damage disclosed by scientific research for the Sponsor as 'verrichter' in the meaning of said Act in each year of insurance coverage.

The insurance applies to the damage that becomes apparent during the study or within 4 years after the end of the study.

10.2 Study funding

CHDR is the sponsor of the study and is funding the study.

10.3 Data handling and record keeping

10.3.1 Data collection

Data will be recorded on electronic data collection forms in Promasys for subsequent tabulation and statistical analysis. The data will be handled confidentially and if possible anonymously.

A Subject Screening and Enrolment Log will be completed for all eligible or non-eligible subjects with the reasons for exclusion.

Some of the neuropsychological assessment are recorded on paper data collection forms and will be entered after quality control in a Promasys database for tabulation and statistical analysis.

10.3.2 Database management and quality control

All data from paper source will be entered into the Promasys database twice, by two different individuals. A quality control check will be done by CHDR staff on all data entered in the Promasys database, using data entry progress checks and database listings (blind data review). Errors with obvious corrections will be corrected before database lock.

Results of computer (NeuroCart) tests and electronically captured questionnaires and clinical laboratory will be sent electronically to CHDR and loaded into the database.

After the database has been declared complete and accurate, the database will be locked. Any changes to the database after that time can only be made by joint written agreement between the investigator and the statistician.

10.4 Access to source data and documents

All study data will be handled confidentially. The investigator will retain the originals of all source documents generated at CHDR for a period of 2 years after the report of the study has been finalised, after which all study-related documents will be archived (at a minimum) on micro-film which will be kept according to GCP regulations.

The investigator will permit trial-related monitoring, audits, EC review and regulatory inspections, providing direct access to source data and documents.

10.5 Quality control and quality assurance

This study will be conducted according to applicable Standard Operating Procedures (SOPs). Quality assurance will be performed under the responsibility of CHDR's Quality Assurance manager.

10.6 Protocol amendments

Any change to a protocol has to be considered as an amendment.

10.6.1 Non-substantial amendment

Administrative or logistical minor changes require a non-substantial amendment. Such changes include but are not limited to changes in study staff or contact details or minor changes in the packaging or labelling of study drug. Non-substantial amendments will be approved (signed) by the investigator(s) and will be recorded and filed by the investigator but will not be notified to the EC and the CA.

The implementation of a non-substantial amendment can be done without notification to the appropriate EC or CA. It does not require their approval.

10.6.2 Substantial amendment

Significant changes require a substantial amendment. Significant changes include but are not limited to: new data affecting the safety of subjects, change of the objectives/endpoints of the study, eligibility criteria, study assessments/procedures, study duration, with or without the need to modify the core Subject Information and Informed Consent Form.

Substantial amendments are to be approved by the appropriate EC and the CA will need to provide a 'no grounds for non-acceptance' notification prior to the implementation of the substantial amendment.

Urgent amendment

An urgent amendment might become necessary to preserve the safety of the subjects included in the study. The requirements for approval should in no way prevent any immediate action being taken by the investigators in the best interests of the subjects. Therefore, if deemed necessary, an investigator can implement an immediate change to the protocol for safety reasons. This means that, exceptionally, the implementation of urgent amendments will occur before submission to and approval by the EC(s) and CA.

10.7 End of study report

The investigator will notify the EC of the end of the study within a period of 8 weeks. The end of the study is when 200 subjects have had their study visit.

In case the study is ended prematurely, the investigator will notify the EC, including the reasons for the premature termination.

Within one year after the end of the study, the investigator will submit a final study report with the results of the study, including any publications/abstracts of the study, to the EC. The principal investigator will be the signatories for the study report.

